5.1.8 Allowed Medication

The following medications are allowed during this study:

- 1. Current or other FDA-approved monotherapy ADHD medication (the ongoing medication will not be adjusted during the study).
- 2. EMLA (lidocaine 2.5% and prilocaine 2.5%) or other numbing cream for pharmacokinetic venipuncture.
- 3. Benztropine is permitted for the treatment of emerging EPS at a starting dose of 0.5 mg BID up to a range of 1 to 4 mg/day. Lorazepam (1 to 2 mg per dose not to exceed 3

- times daily) and clonazepam (0.25 to 1 mg per dose not to exceed twice daily) is also permitted to treat EPS.
- 4. For the treatment of akathisia, propranolol is recommended, up to 90 mg/day in divided doses, 3 times per day, starting at 10 mg twice daily and up to 30 mg 3 times daily, as needed.
- 5. Common over-the-counter (OTC) therapies for minor transient ailments (e.g., acetaminophen for headache, ibuprofen for fever) will be allowed without exception.
- 6. Treatment for AEs other than EPS or minor transient ailments is permitted in consultation with the Medical Monitor and Sponsor.

All concomitant medications as well as the dosing of the FDA-approved ADHD medication will be recorded in the electronic case report form (eCRF).

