6.3.2.2 Other Events Requiring Immediate Reporting

The Investigator must report a **pregnancy** that occurs in a subject during a clinical study to the Drug Safety Contact within 24 hours of first becoming aware of the event. Pregnancy should be reported on a Pregnancy Report Form. The Investigator should discuss the case with the Sponsor Medical Monitor; the Investigator must also follow any pregnant subject for 3 months after the child is born. Any AEs concerning the health of the subject during pregnancy or the child after birth must be documented and reported to the Sponsor.

Treatment-emergent **EPS** (e.g., akathisia, dystonia, parkinsonism, tardive dyskinesia), and neuroleptic malignant syndrome should in addition to documenting in the CRF, be reported to the Drug Safety Contact by faxing or scanning the appropriate completed form/source documentation within 24 hours of first becoming aware of the event. EPS incidence will be summarized and shared with study Investigators throughout the clinical trial.

Overdosage of molindone presumably may be manifested by severe EPS and sedation. Coma with respiratory depression and severe hypotension resulting in a shock-like syndrome could occur. In the event of a suspected overdose, the parent or legal representative should be instructed to call 911 or their local poison control center at

Symptomatic, supportive therapy should be the rule. Gastric lavage is indicated for the reduction of absorption of SPN-810, which is freely soluble in water. Since the adsorption of SPN-810 by activated charcoal has not been determined, the use of this antidote must be considered of theoretical value.

Emesis in a comatose patient is contraindicated. Additionally, while the emetic effect of apomorphine is blocked by SPN-810 in animals, this blocking effect has not been determined in humans.

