6.3.3 Management of Treatment-Emergent Extrapyramidal Symptoms

If a subject experiences treatment-emergent EPS (including akathisia, dystonia, parkinsonism, or tardive dyskinesia), benztropine will be permitted at a starting dose of 0.5 mg BID up to a range of 1 to 4 mg/day. Lorazepam (1 to 2 mg per dose not to exceed 3 times daily) and clonazepam (0.25 to 1 mg per dose not to exceed twice daily) will also be permitted to treat the occurrence of EPS. For the treatment of akathisia, propranolol is recommended up to 90 mg/day in divided doses, 3 times per day, starting at 10 mg twice daily and up to 30 mg three times daily, as needed.

A positive finding on an EPS safety assessment scale (Barnes Akathisia Rating, Simpson-Angus, or AIMS) does not necessarily equate to an EPS event. Investigators should evaluate positive findings on the EPS safety assessment scales and integrate them into a global clinical observation to determine if an AE of EPS should be recorded.

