7.5.2 GABA and Glutamate Concentrations

The concentrations of GABA and Glu in the ACC will be obtained during MRS acquisition. The descriptive analyses will be used to examine the concentrations of GABA and Glu by treatment group and visit (pretreatment at Visit 2 fMRI scan and post-treatment at Visit 5). The change from baseline (Visit 5 – Visit 2) in concentration of GABA and Glu will also be assessed for each treatment group.

7.6 **Safety Analysis**

Evaluation of safety will be performed for the safety population. Safety data that will be evaluated include AEs, clinical laboratory results, vital signs, ECGs, and findings from the physical examinations. The occurrence of neurological side effects will be assessed by looking at any worsening in scores from Visit 1 to the end of the study visit for each of the Simpson-Angus Scale, Barnes Akathisia Rating Scale, and AIMS. Suicidal ideation and suicidal behavior will be measured by the C-SSRS.

All summary tables related to safety analyses will use the safety population.

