7.6.1 Adverse Events

AEs will be classified into standardized medical terminology from the verbatim description (Investigator term) using the Medical Dictionary for Regulatory Activities (MedDRA V22.0). AEs will be summarized using discrete summaries at the subject and event level by system organ class and preferred term for each group of doses. Similarly, treatment-emergent AEs will be summarized by severity and relationship separately. Verbatim description and all MedDRA level terms, including the lower-level terms, for all AEs will be contained in the subject data listings.

All AEs occurring throughout the study period will be recorded. Treatment-emergent AEs (TEAEs) will be collected starting after the baseline fMRI scan and after the first dose of study medication (after Visit 3) to the end of the study. These AEs include those that emerge after the fMRI procedures and during treatment or worsen in severity during treatment. These AEs will be tabulated, listed, and analyzed.

Separate TEAE incidence tables will be presented for the 2 treatment groups. The incidence rates for all SADRs will also be summarized as described for all TEAEs.

In addition, these same tables will be presented by treatment period (Titration, Maintenance, and combined Titration and Maintenance periods). For the combined Titration and Maintenance periods, the incidence of TEAEs will also be presented by highest severity reported and the dose of study

medication at first occurrence. Listings (and tabular summaries, if warranted) of deaths, other SAEs, and other significant TEAEs, including TEAEs resulting in treatment discontinuation, will be provided.

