7.6.7 Extrapyramidal Symptoms

The occurrence of neurological side effects will be assessed by examining the observed score at each visit and change from baseline at each post-baseline (Visit 4 and Visit 6) for the Simpson-Angus Scale, Barnes Akathisia Rating Scale, and AIMS.

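### The EPS scale summaries take no account of permitted rescue drugs, and no planned table counts children with any EPS by arm

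*SAP*

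**What the plan says.** **Scales.** SAP 7.6.7 handles the three EPS scales by "examining the observed score at each visit and change from baseline at each post-baseline (Visit 4 and Visit 6"). The opening text of SAP 7.6 adds that neurological side effects will be "assessed by looking at any worsening in scores from Visit 1 to the end of the study visit". Neither place mentions rescue medication. Protocol 8.3.8 had also asked, item by item, for the number and percentage of children scoring worse than baseline at any later visit, with a listing of them. SAP 7.6.7 does not carry this over, and SAP Section 1 says that the SAP replaces the protocol's statistical methods.

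**Rescue.** Protocol 5.1.8 states that "Benztropine is permitted for the treatment of emerging EPS" and also allows lorazepam and clonazepam. Protocol 6.3.3 repeats this ("If a subject experiences treatment-emergent EPS (including akathisia, dystonia, parkinsonism, or tardive dyskinesia), benztropine will be permitted") and adds: "For the treatment of akathisia, propranolol is recommended". No interval between a rescue dose and a scale rating is given.

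**Adverse events and drugs.** SAP 7.6.1 says that "AEs will be summarized using discrete summaries at the subject and event level by system organ class and preferred term". It records AEs over the whole study and tabulates treatment-emergent AEs (TEAEs) by arm and treatment period. It defines no EPS group of terms. On drugs, protocol 5.1.8 says "All concomitant medications as well as the dosing of the FDA-approved ADHD medication will be recorded in the electronic case report form (eCRF"), and SAP 7.2 includes concomitant medications among the safety-population tables, with no link to EPS.

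**The concern.** Occurrence is cumulative: did this child have EPS at any time on study drug? The scale summaries are readings on two days. Between first dose and the first of those days, a child can develop EPS, be treated for it, and be rated with the signs suppressed. The more effective the treatment, the smaller the reported scale change.

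Protocol 3.1 says these scales were chosen specifically to monitor EPS, so a reader will look there for the EPS result. Understatement would fall mainly on whichever arm has more treated EPS. In a small descriptive trial with no hypothesis tests, a plain count of affected children per arm is the most useful EPS result available, and no planned table gives it.

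**Working it through.** The plan states no figure on this point, so there is none to reproduce. The check is of timing, then of what each planned output shows, then an illustration on assumed inputs.

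**1. Timing.** Titration runs Day 1 to 14 and maintenance Day 15 to 28 (protocol 3.5). The first on-treatment scale rating is Visit 4, Day 21 (protocol 4.2.4). The second is Visit 6, about Day 35, after a week of taper or conversion (protocol 3.7). A child who stops during titration is rated at a final visit within a week of stopping (protocol 4.2.6). Each rating can follow both the EPS and its treatment.

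**2. What each output shows for a child with EPS treated successfully before Visit 4.**
- Scale scores and change (SAP 7.6.7): can be at or near baseline.
- Worsening to the end-of-study visit (SAP 7.6): can be absent for the same reason.
- TEAE tables (SAP 7.6.1): the event is present, under its own preferred term.
- Concomitant medication table (SAP 7.2): the drug is present, not tied to EPS.
- Number of children per arm with any EPS: not planned.

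Restoring the count in protocol 8.3.8 would not by itself close the gap, because a child rated normal on rescue does not score worse.

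**3. Illustration of masking.** Input from protocol 4.1: 15 children in the SPN-810 arm. Assumed: EPS risk p, and share m of EPS cases whose score is back at baseline when rated. Also assumed: no worsening without EPS, and every EPS case recorded as an AE.

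Expected EPS cases = 15p. Expected worse scores = 15p(1 − m). Chance of at least one worse score = 1 − [1 − p(1 − m)]^15. For p = 20% and m = 80%: 15 × 0.20 × 0.20 = 0.60, and 1 − 0.96^15 = 0.458.

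| p | EPS cases expected | Worse scores expected, m = 0 / 50% / 80% / 100% | Chance of at least one worse score |
|---|---|---|---|
| 5% | 0.75 | 0.75 / 0.38 / 0.15 / 0 | 0.537 / 0.316 / 0.140 / 0 |
| 10% | 1.50 | 1.50 / 0.75 / 0.30 / 0 | 0.794 / 0.537 / 0.261 / 0 |
| 20% | 3.00 | 3.00 / 1.50 / 0.60 / 0 | 0.965 / 0.794 / 0.458 / 0 |
| 30% | 4.50 | 4.50 / 2.25 / 0.90 / 0 | 0.995 / 0.913 / 0.605 / 0 |

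The second column does not depend on m: under these assumptions, a count that includes EPS AEs recovers 15p whatever the masking.

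**4. Illustration on means and rows.** Assume that 3 of 15 children (20%) have EPS, each worth 4 Simpson-Angus points. The arm mean change is then 4 × 3/15 = 0.8 with no masking and 0 with complete masking. If the three events carry three different preferred terms, each row shows 1/15 = 6.7% and no preferred-term row shows 20%. At an assumed 8 per arm, the rows show 1/8 = 12.5% against 3/8 = 37.5%.

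**The case against.** The strongest reply is that the event is not lost. EPS that prompts treatment meets the AE definition in protocol 6.3.1. Protocol 6.3.2.2 requires it to be documented in the case report form and reported within 24 hours, and SAP 7.6.1 tabulates it by arm and period, including titration. A reader might infer that treated EPS ends up recorded as little or no EPS. The documents do not support that: masking affects the scale summaries only.

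A reader might also infer that SAP 7.6.7 declares a child with a normal score free of EPS. It does not. It describes scores, and protocol 6.3.3 says that a positive scale finding need not be an EPS event and leaves that decision to global clinical observation.

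Nor does the SAP break a promised table. The statement that "EPS incidence will be summarized and shared with study Investigators throughout the clinical trial" describes communication to investigators who are blinded (protocol 5.1.7), not an analysis by arm.

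Three further points have weight. The system organ class row counts children, so events sharing a class would be added together there, though mixed with non-EPS events. SAP 6.1 provides subject listings, in which individual cases among about 30 children can be found. And the background is mixed: protocol 1.4 and 1.5 describe little EPS with molindone, while protocol 3.1 cites greater risk in youths on antipsychotics.

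What survives is narrower. No rule covers scores taken on rescue, and a reader wanting EPS by arm must assemble it from listings.

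**Conclusion.** The point holds as a gap in analysis and reporting, not in data capture. The scale summaries in SAP 7.6.7 can understate EPS that occurred and was treated, and no planned table gives an EPS-only count of children by arm. The protocol's any-worsening count and listing have also been dropped; SAP 7.6 keeps only a general statement about worsening to the end-of-study visit.

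The size cannot be derived from the documents. On the assumed inputs, it runs from none to all of the scale signal. The 20%, 4-point and 8-per-arm figures are assumptions for illustration, not estimates. Understatement that favours SPN-810 would further require treated EPS to be commoner in that arm, which is plausible but not established here. SAP 6.1 makes every analysis descriptive after early termination, so no test result depends on this. It is a cheap improvement worth making.

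**What to change.** Add to SAP 7.6.7 one by-arm table for the safety population: the number and percentage of children with any of

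- (a) a TEAE in a pre-listed EPS group (akathisia, dystonia, parkinsonism, tardive dyskinesia and their component terms);
- (b) recorded use of a drug given for EPS;
- (c) a worse scale score at any post-baseline visit, as in protocol 8.3.8.

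Show each component separately as well. Component (c) can be met without clinical EPS: the Simpson-Angus has 10 items and the AIMS 12, and a one-point change on any item would qualify.

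Flag scale scores taken while on such a drug and repeat the scale summary without them as a sensitivity display. It is not a correction, because it removes children who had EPS; the any-EPS count is the main repair.

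The cost is the extra table, the repeated display, and a review of the term list and drug indications. The review should be blinded if that is still possible; SAP 6.1 already writes of the imaging analysis in the past tense. The documents do not say that the eCRF records indication. Where it is missing, the table should say so.

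Two inconsistencies touch this table. Protocol 5.1.9 prohibits benzodiazepines on study, while 5.1.8 and 6.3.3 permit lorazepam and clonazepam for EPS; these passages must be reconciled. Protocol 6.3.9 places the three scales at Visit 1, but the Visit 1 procedure list in 4.2.1 omits them, so the baseline for component (c) should be confirmed.

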7.7 Tertiary Variable Analysis

7.7.1 Pharmacokinetic Analysis

PK analysis will not be conducted.

7.7.2 Behavioral Scales

Each of 3 variables (R-MOAS, CGI-I, and CGI-S) will be assessed based on the completed population. The descriptive statistics will be reported for observed value and change from baseline for each measurement at each visit for both study treatment groups.

8 VALIDATION

The TLFs will be checked for completeness and consistency before finalization.
